Principal investigator: [name]

Protocol Title: Assessing Cognitive Improvements, Brain Neuroplasticity and the Role of Genetic Factors After Aerobic Exercise in Sedentary Adults

IRB Number: 20180926

NCT: NCT03804528

Document Version Date: 2/22/2021

IRB Study Number: 20180926

1) Protocol Title

Assessing Cognitive Improvements, Brain Neuroplasticity and the Role of Genetic Factors After Aerobic Exercise in Sedentary Adults

2) Objectives

The overall goal of the proposed study is to evaluate the effects of an 8-week aerobic exercise program on cognition and determine the relationship between cognitive improvements and neuroplasticity. Limited to Option A (See Study Options section), we will also explore the effect modification of BDNF levels and BDNF allelic status, and APOE4 status on cognitive response after exercise.

Aim 1: Quantify improvements in cognitive performance after 8 weeks (150 min per week) of moderate intensity aerobic exercise in sedentary adults ≥ 55 years of age. **H1:** We hypothesize that we will see improvements in overall cognitive performance after exercise, and greater improvements in some of the cognitive domains (e.g., in executive function and processing speed, as opposed to memory or language).

Aim 2: Determine an association between changes in plasticity, aerobic capacity, and cognitive performance overall and by cognitive domain, after 8 weeks of moderate intensity aerobic exercise in sedentary adults ≥ 55 years of age. **H2:** We hypothesize that a greater response in the brain plasticity will be associated with greater improvements in cognitive performance overall and in executive function after exercise.

Aim 3 (Option A): Explore the effect modification of BDNF (levels and Val66Met) and APOE e4 on cognitive response after exercise. **H3:** We hypothesize that individuals with greater levels of BDNF, being Val carriers or APOE e4 carriers will have greater improvement in cognitive performance after exercise.

3) Study Plan/Options

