 - d. Any medical devices (i.e. Cardiac pacemaker, deep brain stimulator, medication infusion pump, cochlear implant, vagal nerve stimulator)
 - e. Intracranial lesion
 - f. Substance abuse or dependence within the past six months
 - g. Exclusively for Option A: TMS Neuroplasticity assessment, as per the TMS Safety Guidelines.¹³
 - i. History of fainting spells of unknown or undetermined etiology that might constitute seizures
 - ii. History of seizures, diagnosis of epilepsy, history of abnormal (epileptiform) EEG or family history of treatment resistant epilepsy

IRB Study Number: 20180926

- Pregnant women
- Vulnerable populations such as prisoners
- People unable to consent themselves
- Subjects who, in the Investigator's opinion might not be suitable for the study

[figure not shown]
6) Number of Subjects

This is not a multi-center study. We will recruit a total of 80 adults. We will use a multifaceted approach by recruiting participants from the Evelyn F. McKnight Brain Institute community memory clinic, and by advertising the study using flyers throughout the University of Miami Miller School of Medicine (UMMSM) and Coral Gables Campuses, the Miami community and participant registries. We will also recruit via online research database tool including the ResearchMatch.org. In addition, we will access University Research Informatics Data Environment (URIDE), and potential subjects will be identified and contacted via the Consent to Contact Initiative.

With a significance level of 0.05, our sample of 80 individuals will provide 80% power to detect a Cohen effect size of 0.36 using a two-sided paired t-test for Aim 1, the effect size associated with improvements in executive function in a recent meta-analysis of healthy adults 55+,²⁶ and an attrition of 20%, not uncommon in exercise intervention trials. In addition, a sample of 80 participants will provide 80% power to detect a correlation of 0.34 between the change in neuroplasticity and the change in cognitive performance.

7) Study Timelines

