- A virtual consenting process will be completed using zoom for healthcare and REDCap e-consent as approved through the Clinical and Translational Science Institute (CTSI). The individual will be sent a REDCap link either through a secure email or through the chat feature of zoom. Once the individual opens the link, they will be asked to share their screen. At that time a trained study personnel will review the informed consent with the individual and answer any question the individual may have about the study. If the individual agrees to participate in the study, they will be asked to sign the e-consent form and provide the study personnel remote access of their web browser to also sign the consent form. The individual will then certify the information and submit the consent. At that time, they will have the option to download or print the completed consent form. A copy can be mailed at the individual's request. Participants will then be mailed a study kit.

Session #1b: Familiarization session- Review items delivered to place of residence using secured zoom (estimated time: 1.5 hours, completed in week one, follow up session may be scheduled as needed)

- Familiarize participant with all of the tools in the study kit.

IRB Study Number: 20180926

- The participant will learn to take their own blood pressure, oxygen saturation, put on the heart rate monitor, and proper safety and cleaning procedures.
- Participants will learn various zoom functions such as sharing screens which will be later utilized in the study.
- Participant will learn how to put on the EEG cap and how to operate the tablet.

Session #2 and #28 Pretest and Post assessment Part 1 (estimated time: 2 hours, completed in week 1)

- TMS plasticity assessment will be replaced with the tACS/EEG plasticity assessment.
- TMS-EEG will not be offered for Option B of the study.

Session #29 Posttest assessment- Part 2 (estimated time: 2 hours, completed in week 1).

- Return Study Kit.

8) Study Endpoints

Neuroplasticity Measures

- **TMS Plasticity Measures**
 - An index of the duration of the TBS-induced modulation of corticospinal excitability (the time-point at which the normalized mean MEP amplitude returns to baseline values) will be defined for each participant.
- **TMS-EEG**

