With a significance level of 0.05, our sample of 80 individuals will provide 80% power to detect a Cohen effect size of 0.36 using a two-sided paired t-test for **Aim 1**, the effect size associated with improvements in executive function in a recent meta-analysis of healthy adults 55+,⁴² and an attrition of 20%, not uncommon in exercise intervention trials. In addition, a sample of 80 participants will provide 80% power to detect a correlation of 0.34 between the change in TMS neuroplasticity and the change in cognitive performance for **Aim 2**, and 80% power to detect an R-Squared of 0.11 attributed to a genetic modification in the change in cognitive performance using an F-Test for **Aim 3 (Option A only)**. We expect an overall improvement in cognitive performance after aerobic exercise. Most robust improvements are expected in executive function as previously shown in elderly, but also in other cognitive domains such as processing speed and attention.¹¹

Baseline characteristics will be summarized as means \pm standard deviation or medians (interquartile ranges) for continuous variables and as frequency (%) for categorical variables. Normality for the distributions of continuous variables will be visually assessed and statistically tested. If the normality assumption is questionable, Box-Cox transformation will be used to reduce the skewness in the indicated analyses or non-parametric tests will be used. All statistical tests will be conducted against a 2-sided alternative hypothesis, employing a significance level of 0.05.

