In the univariate analysis, we will compare the cognitive performance (overall and by domain) before and after exercise, using paired t-test to test for **Specific Aim 1**. For **Specific Aim 2**, we will examine the relationship between the change in TMS neuroplasticity and the change in cognitive performance using Pearson product-moment correlation coefficient. For **Specific Aim 3**, we will compare mean change in cognitive performance across subgroups by genotype using F- test. In the multivariable analyses, we will adjust for baseline characteristics (age, sex, race- ethnicity, education) using mixed effect modeling to quantify improvements in cognitive performance after exercise (**Specific Aim 1**), and to determine an association between changes in TMS plasticity, cognitive performance and changes in aerobic capacity (**Specific Aim 2**). We will use modification models by including interaction terms (time-by-genotype) to explore the relationship between change in cognitive performance after exercise and BDNF levels, Val66Met, and APOE e4 status (**Specific Aim 3-Option A only**).

12) Provisions to Monitor the Data to Ensure the Safety of Subjects*

Monitoring the safety of participants with respect to TMS neuroplasticity assessment

TMS has been used in a growing number of laboratories worldwide since 1984. A series of adverse events have been identified since then, and have been thoroughly reviewed for the development of recommended safety guidelines and precautions for the use of TMS, first at a consensus conference at the NIH in June, 1996 and, more recently, in 2008 in Siena (Italy), in a

IRB Study Number: 20180926

meeting of an international panel of TMS experts ([The Safety of TMS Consensus Group](#)).

The principal investigator will ensure that these guidelines are well-known by all study investigators and will carefully follow these updated safety guidelines in the present study. Additionally, we will track and report any adverse events that may occur.

Monitoring the safety of participants with respect to tACS neuroplasticity assessment

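### Aim 2 is powered and analysed on TMS plasticity with 80 participants, but Option B has no TMS and the plan gives no rule for combining the two plasticity indices

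*Combined protocol and SAP*

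**What the plan says.** Section 11, Data Analysis, words Aim 2 on TMS three times. The power statement claims "80% power to detect a correlation of 0.34 between the change in TMS neuroplasticity and the change in cognitive performance" from 80 participants. The univariate analysis reads "we will examine the relationship between the change in TMS neuroplasticity and the change in cognitive performance using Pearson product-moment correlation coefficient". The mixed model is "to determine an association between changes in TMS plasticity, cognitive performance and changes in aerobic capacity", adjusted for age, sex, race-ethnicity and education only.

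Elsewhere the wording is wider. Section 2 sets Aim 2 as "Determine an association between changes in plasticity, aerobic capacity, and cognitive performance overall and by cognitive domain", without naming TMS. Section 6 repeats the power claim as "80% power to detect a correlation of 0.34 between the change in neuroplasticity and the change in cognitive performance", again without TMS. Section 4 asserts that the two stimulation methods give comparable data.

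Section 7 (Option B) says that "TMS plasticity assessment will be replaced with the tACS/EEG plasticity assessment". Section 3 makes Option B the only option until Option A may resume, and section 9 keeps it open afterwards by participant preference. No expected split is given. Where an aim is meant for one option, the plan marks it: "Aim 3 (Option A): Explore the effect modification of BDNF" is labelled in sections 2 and 11. Aim 2 carries no such label.

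**The concern.** As worded, the Aim 2 analysis has no plasticity variable for an Option B participant. Two readings are open: Option B drops out of Aim 2, or its index is put into the same correlation. The plan does not choose, and gives no rule for the second.

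All three Aim 2 variables differ by option.

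- **Plasticity.** Option A uses a duration after theta burst stimulation of the motor cortex, "the time-point at which the normalized mean MEP amplitude returns to baseline values". Option B uses a change in resting EEG after stimulation over the frontal lobe, with no unit or formula given.
- **Cognition.** Option B drops the Stroop test and adds TestMyBrain tests, while Aim 2 is to be examined by domain. The domain affected is itself unclear: section 8 lists Stroop under processing speed, section 9 under response inhibition, flexibility and attentional control.
- **Aerobic capacity.** Option A uses the shuttle walk, Option B one-minute sit-to-stand repetitions.

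Option is not randomised and not adjusted for. At stake are the stated power and, under raw pooling, whether a correlation reflects biology or merely the difference between two groups measured in different ways.

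**Working it through.** **Inputs from the documents:** two-sided alpha 0.05; r = 0.34; 80 enrolled; 20% attrition (given in the Aim 1 sentence), so 80 × 0.8 = 64 completers. **Assumptions, because the documents give no values:** option split, ratio of SDs between the two indices, mean shifts between options, and the correlation in Option B.

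**1. The plan's figure.** Fisher z: power = Φ(atanh(r)·√(n−3) − 1.96), with atanh(0.34) = 0.354.

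- n = 80: 0.354 × 8.775 = 3.107, power 87.4%.
- n = 66: 0.354 × 7.937 = 2.811, power 80.2%.
- n = 64: 0.354 × 7.810 = 2.766, power 79.0%.

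The stated 80% is therefore reproduced at 64 completers, all on one measure. It already allows for attrition. Even with no attrition, 66 of 80 (82%) must have TMS, so 80% is lost once more than 14 take Option B.

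**2. TMS data only.** Same formula, 64 completers in all:

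| Option A share (assumed) | Option A completers | Power at r = 0.34 | r detectable at 80% power |
|---|---|---|---|
| 90% | 58 | 75% | 0.36 |
| 75% | 48 | 66% | 0.39 |
| 50% | 32 | 48% | 0.48 |
| 25% | 16 | 25% | 0.65 |

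**3. Raw indices pooled in one Pearson correlation** (simulation, bivariate normal).

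- True r = 0.34 in both options, 32+32, no mean shift: power about 79%, 75%, 70% or 56% at SD ratios of 1, 2, 3 or 10.
- True r = 0, with option shifts (plasticity/cognition, in SD) of 0.3/0.3, 0.5/0.5 or 1.0/0.5: false positives about 5%, 8% or 14% at 32+32, and 5%, 5% or 6% at 58+6.

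Pooling loses nothing if scale, means and correlation match across options.

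**4. Options combined within strata.** z = [(nA−3)·atanh(rA) + (nB−3)·atanh(rB)] / √(nA+nB−6).

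- rA = rB = 0.34, 64 completers, any split: 0.354 × √58 = 2.697, power 77%. A correlation standardised within option gives about 78% by simulation.
- Same correlations, no attrition (80 analysed): 0.354 × √74 = 3.046, power 86%.
- 32+32 with rA = 0.34: power 89%, 52% or 27% if rB is 0.45, 0.17 or 0.

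Against TMS only at the four splits (58+6, 48+16, 32+32, 16+48), combining gives 75%, 67%, 52% and 37% if rB = 0.17, which equals or beats TMS only (75%, 66%, 48%, 25%). If rB = 0 it gives 73%, 55%, 27% and 9%, which is worse at every split.

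**5. Testing whether the two correlations differ.** SE = √(1/(nA−3) + 1/(nB−3)). At 32+32, power is 11% or 27% for rB = 0.17 or 0. A non-significant difference would therefore not show that the correlations are equal.

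**The case against.** The best case for the plan is that TMS is leftover wording from before Option B was added. Sections 2 and 6 speak of plasticity or neuroplasticity in general, section 8 defines an index for each option, and section 4 calls the methods comparable, so both options are probably meant to enter. That is the more natural reading, but it does not close the gap. The analysis section then names the wrong variable and lacks the rule for joining a duration to an EEG change.

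It can also be said that section 11 allows a Box-Cox transformation or a non-parametric test if normality is doubtful. That may soften the most extreme SD ratio, where pooled data would look clearly non-normal. It does not put the two indices on a common scale or remove a shift between options.

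Finally, Option B may be small. In-person TMS work was under way before this change, so the Option A share could be high. At 58+6 the harm is modest: 75% power on TMS only, and false positives of 5-6% under pooling. This stands, and limits the size of the problem without supplying the missing rule.

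A reader might infer that the 80% is a miscalculation, that most participants will be in Option B, or that including Option B must cost a great deal of power. The documents support none of these. The arithmetic is right for one measure, no split is given, and combining costs 1-2 points if the correlations match and gains power if Option B's is larger.

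**Conclusion.** Wrong as written, in a limited sense: the stated Aim 2 power, on TMS with 80 participants, is unsupported once Option B takes a material share. What rests on the documents alone is that 80% power needs about 64 to 66 participants on one common measure, that Option B participants do not have the named measure, and that no pooling rule, stratum or option term exists. The rest depends on assumed values: 75% down to 25% power if only TMS data enter; about 75% down to 56% under raw pooling with unequal scales at 32+32; false positives between about 5% and 14% at 32+32 under the assumed shifts. It should be corrected before analysis, because choosing the rule after seeing the data would be an avoidable analytic freedom.

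**What to change.** **Wording.** In section 11, replace TMS neuroplasticity and TMS plasticity with the option-specific plasticity index, and say that both options enter Aim 2. In section 6, which does not mention TMS, state that neuroplasticity means that index. Qualify the comparability claim in section 4.

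**Correlation.** Estimate it within each option with a 95% CI. Combine by Fisher z (weights n−3) or by standardising within option, and always show the between-option difference and its CI beside the combined estimate.

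**Mixed model.** Standardise plasticity and fitness change within option. Use cognitive measures common to both options (Digit Span, Trail Making, RBANS, D-KEFS fluency) or standardise the outcome within option. Include option and option-by-plasticity terms, crossed with time if the outcome is pre/post scores rather than change.

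**Power.** State it conditionally: about 77-78% with 64 completers if r = 0.34 in both options; at 32+32 (Fisher-z combination), 52% or 27% if Option B's r is 0.17 or 0, and 89% if it is 0.45.

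**Alternative.** Label Aim 2 Option A only and give power for the expected number of Option A completers.

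**Cost.** No new data. Combining properly costs 1-2 points of power if the correlations match. Each option alone is imprecise (detectable r 0.48 at 32 completers), and if only common tests are used, Stroop and TestMyBrain are reported within option only.

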For Option B, we will use transcranial alternating current stimulation (tACS), which is one specific form of transcranial electrical stimulation (tES) combined with electroencephalography (EEG) to measure neuroplasticity that is similar to TMS neuroplasticity measurements. In both paradigms, the brain's response to a mild electrical stimulus is recorded. With TMS, a mild electrical stimulus is delivered with electromagnetic induction, and the response is measured with electromyography surface electrodes. With tACS, a mild electrical current is delivered with small electrodes placed on the scalp, and measured with electromyography surface electrodes. These two methods are under the same neurophysiological principles, and thus, yield comparable data.

The practical application of tACS is simple: a low intensity (1-2 mA) alternating electrical current is applied to the scalp to influence underlying cortical excitability, which is measured with non-invasive surface EEG electrodes. Direct current stimulation is presently FDA-approved for extracranial use, and FDA applications for cranial stimulation for management of mood disorder and chronic pain are in progress. The stimulator used in this study is the STARSTIM®-Home system (Neuroelectrics, Inc), a tES home-base system that recently received FDA approval for the Investigational Device Exemption supplemental protocol in a study for tES to be used to treat patients with Major Depression Disorder (MDD) due to COVID-19 related restrictions. STARSTIM®-Home system is capable of recording EEG before, during and after tACS stimulation.

Genetic factors may modify cognitive response to exercise. A common single nucleotide polymorphism of the BDNF gene (Val66Met) impairs activity-dependent release of BDNF.¹⁹ We and others have demonstrated that the Val66Met allele attenuates improvements in cognitive performance after exercise, both in young^{18,20} and old adults²¹. Furthermore, carriers of the apolipoprotein E (APOE) e4 alleles exhibit greater cognitive benefits after exercise through unknown mechanisms,^{22,23} although

IRB Study Number: 20180926

they have greater risk for AD.^{24,25} The effects of genetic factors on response to exercise will only be evaluating in the Option A.

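### The 80% power stated for Aim 3 is figured on all 80 participants, though Aim 3 is Option A only with no stated degrees of freedom, and H3's BDNF grouping conflicts with its rationale

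*Combined protocol and SAP*

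**What the plan says.** Section 11 (Data Analysis) gives the Aim 3 power as "80% power to detect an R-Squared of 0.11 attributed to a genetic modification in the change in cognitive performance using an F-Test for" Aim 3, which it labels Option A only. The same sentence opens "In addition, a sample of 80 participants will provide 80% power to detect a correlation of 0.34", so the Aim 3 figure rests on the full 80. The preceding sentence allows for "an attrition of 20%, not uncommon in exercise intervention trials". The testing rule is "All statistical tests will be conducted against a 2-sided alternative hypothesis, employing a significance level of 0.05".

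The univariate analysis for Aim 3 is "we will compare mean change in cognitive performance across subgroups by genotype" by F-test. The multivariable analysis adds time-by-genotype interaction terms. Neither states how many genotype groups are formed, how Val66Met is coded, or the numerator degrees of freedom.

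Section 2 states H3 as an expectation that people with higher BDNF levels, or "being Val carriers or APOE e4 carriers will have greater improvement in cognitive performance after exercise". Section 4 gives the BDNF rationale: the polymorphism impairs activity-dependent release of BDNF, and "the Val66Met allele attenuates improvements in cognitive performance after exercise".

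Section 3 makes Option B the only route until in-person work is approved again. Section 9 (Methods) keeps Option B available by preference after that. Section 7 drops genetic testing from Option B, and section 14 lists blood collection under Option A only. Section 6 sets one total of 80 and does not divide it between the options.

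**The concern.** Two things do not fit together.

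First, the power statement counts people who cannot contribute. Every Option B participant among the 80 lacks a genotype, so Aim 3 can reach 64 completers only if everyone is in Option A. The power also depends on the numerator degrees of freedom, which are left open. Anyone using this figure to interpret a null genetic result, or to plan the follow-on grant application mentioned in section 4, would overrate what Aim 3 can detect.

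Second, H3 and the background point to different groupings. If the variant allele attenuates the response, heterozygotes should show attenuation. Val carriers, read literally, are Val/Val plus Val/Met, so heterozygotes fall in the group expected to benefit and only Met/Met remains for comparison. The analysis section does not settle the matter, so several groupings stay open until after the data are seen.

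**Working it through.** **Inputs from the documents.** N = 80 and attrition 20%, so 80 × 0.8 = 64 completers; R² = 0.11; alpha 0.05; stated power 80%; Aim 1 effect size 0.36; Aim 2 correlation 0.34. **Not in the documents, so assumed:** numerator df (1 or 2), Option A completers (48, 40, 32) and Met allele frequency q (0.1 to 0.3, Hardy-Weinberg proportions).

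**Step 1: which N underlies the paragraph?** The two companion figures give:

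| Figure | N = 64 | N = 80 |
|---|---|---|
| Paired t-test, d = 0.36 (noncentral t, d√N) | 80.9% | 88.9% |
| Correlation 0.34 (Fisher z, √(N − 3)) | 79.0% | 87.4% |

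Both match 80% at 64 and not at 80.

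**Step 2: the Aim 3 figure.** f² = R²/(1 − R²) = 0.11/0.89 = 0.1236; noncentrality λ = f²N; df1 = u; df2 = N − u − 1. Power is the probability that a noncentral F exceeds the 0.05 critical value.

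| N analysed | λ | u = 1 | u = 2 |
|---|---|---|---|
| 80 | 9.89 | 87.4% | 79.4% |
| 64 | 7.91 | 79.1% | 68.9% |

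Two routes reproduce the stated 80%: 1 df at 64, or 2 df at 80. The first agrees with the attrition allowance and with step 1.

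**Step 3: Option A only.** The same formula at assumed numbers of Option A completers:

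| Completers | Power, u = 1 | Power, u = 2 | R² detectable at 80% power, u = 1 |
|---|---|---|---|
| 64 (all in Option A) | 79.1% | 68.9% | 0.112 |
| 48 | 66% | 55% | 0.15 |
| 40 | 58% | 47% | 0.17 |
| 32 | 49% | 38% | 0.21 |

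**Step 4: the grouping in H3.** The expected Met/Met count is Nq². Among 64 it is 0.6, 2.6 and 5.8 at q = 0.1, 0.2 and 0.3.

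Suppose the true effect is Val/Val versus any Met with R² = 0.11. The share of that R² kept by a Val-carrier versus Met/Met split is the squared correlation of the two indicators:

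q²(1 − q)² / {(1 − q²)[1 − (1 − q)²]}

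At q = 0.2 this is 0.0256/0.3456 = 0.074. Over q = 0.1 to 0.3 it is 0.043 to 0.095, so the captured R² is 0.005 to 0.010. Power at 64 is about 8% to 13%.

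**Step 5: if the true effect is additive in Met alleles (R² = 0.11).** Val/Val versus any Met keeps 82% to 95% of the R² (power 70% to 77% at 64). Val carriers versus Met/Met keeps 18% to 46% (power 20% to 45%). An allele-count trend keeps all of it (79.1%), and the three-genotype F-test stays at 68.9%.

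**The case against.** The strongest reply is that the plan leaves the genotype analysis undefined, which is not the same as defining it wrongly. Subgroups by genotype could mean two groups, and an F-test on Val/Val versus any Met is then the contrast that the rationale suggests. APOE is framed throughout as e4 carriage or status. A loosely worded hypothesis in section 2 is not a planned test. The rationale gives no mode of inheritance, so an additive coding fits it as well. Aim 3 is also described as exploratory, and no main conclusion rests on it.

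Most of this stands, and it rules out three stronger readings that a reader might infer:

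- **That the stated 80% can only come from a single-df test.** Taken at the literal 80, a 2-df test gives 79.4%. The 1-df reading depends on 64 completers. That is the better reading of the paragraph, but it is an inference.
- **That the plan commits to three BDNF groups, or to testing Val carriers against Met/Met.** Section 11 specifies neither.
- **That the BDNF analysis would come out null whatever the truth.** The 8% to 13% belongs to a contrast inferred from the wording of H3. The F-test that is actually planned keeps about 69% power at 64 completers even with three groups.

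The objection does not answer the denominator problem: the plan labels Aim 3 Option A only and powers it on everyone. Nor does exploratory status account for it, since the plan attaches a directional hypothesis, a named test and a power figure to this aim.

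**Conclusion.** The point holds as a mismatch between a stated power and the people and test it applies to, together with a hypothesis worded against its own rationale.

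The larger part is Option A enrolment. With 1 df, power falls from 79.1% at 64 completers to 49% at an assumed 32, about 30 points. The df question costs about 10 points at 64 (79.1% to 68.9%). The number in Option A is not in the documents, so the range of 32 to 48 is illustrative. The direction is not in doubt: each Option B participant reduces the Aim 3 sample.

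The H3 wording matters only if it is carried into the analysis. The size of that loss depends on assumed allele frequencies of 10% to 30% and on the genetic model, but Val carriers versus Met/Met is the weaker grouping under both models examined. As Aim 3 is exploratory, severity is minor to moderate.

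**What to change.** 1. In section 11, restate the Aim 3 power, or the R-squared detectable at 80% power, for a stated numerator df at the expected number of Option A completers. Do not enrol more participants for this purpose.
2. In section 2, reword H3 to match section 4, so that greater improvement is expected in Val/Val than in carriers of any Met allele.
3. In section 11, define the BDNF test as the 1-df contrast of Val/Val versus any Met, and the APOE test as e4 carrier versus non-carrier. Use the same coding in the F-test and in the time-by-genotype term. Report the three BDNF genotype means descriptively.

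The cost is a few lines of text, with no change to visits, samples or enrolment. The downside is small: the contrast assumes that one Met allele is enough to attenuate the response. An allele-count trend also fits the rationale and could be named as a sensitivity analysis.
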